6.5.1.2 Etoposide/Platinum Chemotherapeutic Agents

For supportive care measures for the management of AEs that may result from treatment with chemotherapy, refer to the approved product labels for these agents.

During Induction (Cycles 1-4), the use of CSFs (G-CSF or GM-CSF) is highly recommended as primary prophylaxis to reduce the risk of febrile neutropenia, especially as many participants have multiple comorbidities and advanced disease. The American Society of Clinical Oncology guidelines for use of CSFs should be followed.

For all agents and administration, antiemetic therapy should follow MASCC guidelines [Roila, F., et al 2016] and should include a 5-HT3 receptor antagonist, dexamethasone (or equivalent) and/or aprepitant as per the MASCC guidelines.

In addition, all participants should receive the appropriate corticosteroid premedications as per the local approved label.

Additional premedications and pre- and post-cisplatin hydration should be administered as per local practice.

6.6 **Dose Modification**

The dose modification and toxicity management guidelines for immune-related adverse events (Table 5) and the infusion reaction dose modification and treatment guidelines (Table 6) apply to both atezolizumab and MK-7684A (ie, blinded study intervention).

Protocol Amendment 04 implementation: Due to discontinuation of experimental arm (Arm A: MK-7684A) and ongoing participants being offered an option to move to the comparator arm (Arm B: atezolizumab monotherapy), the dose management and toxicity management guidelines for atezolizumab should follow approved local label.

6.6.1 Immune-Related Events and Dose Modification (Withhold, Treat, Discontinue)

Dose Modification and Toxicity Management for Immune-related AEs Associated with MK-7684A or Atezolizumab

AEs associated with study intervention exposure may represent an immune-related response. These irAEs may occur shortly after the first dose or several months after the last dose of treatment and may affect more than one body system simultaneously. Therefore, early recognition and initiation of treatment is critical to reduce complications. Based on existing clinical study data, most irAEs were reversible and could be managed with interruptions of study intervention, administration of corticosteroids and/or other supportive care. For suspected irAEs, ensure adequate evaluation to confirm etiology or exclude other causes. Additional procedures or tests such as bronchoscopy, endoscopy, skin biopsy may be included as part of the evaluation.

Attribution of Toxicity:

When study interventions are administered in combination, attribution of an adverse event to a single component is likely to be difficult. Therefore, while the investigator may attribute a toxicity event to study intervention, study intervention must be held according to the criteria in the Dose Modification and Toxicity Management Guidelines for Immune-Related Adverse Events.

Holding Study Interventions:

When study interventions are administered in combination and if the AE is considered immune-related, study intervention should be held according to recommended Dose Modification criteria.

If the toxicity does not resolve or the criteria for resuming treatment are not met, the participant must be discontinued from study intervention.

Restarting Study Interventions:

Participants may restart study intervention as described below:

If the toxicities do resolve and conditions are aligned with what is defined in the Dose Modification and Toxicity Management Guidelines for irAEs, study intervention may be restarted at the discretion of the investigator.

Dose Modification and Toxicity Management Guidelines for irAEs associated with MK-7684A or atezolizumab are provided in Table 5.

Table 5Dose Modification and Toxicity Management Guidelines for Immune-related Adverse Events Associated with
MK-7684A or Atezolizumab

General instructions:

- 1. Severe and life-threatening irAEs should be treated with IV corticosteroids followed by oral steroids. Other immunosuppressive treatment should begin if the irAEs are not controlled by corticosteroids.
- 2. Study intervention must be permanently discontinued if the irAE does not resolve or the corticosteroid dose is not ≤10 mg/day within 12 weeks of the last treatment.
- 3. The corticosteroid taper should begin when the irAE is \leq Grade 1 and continue at least 4 weeks.
- 4. If study intervention has been withheld, treatment may resume after the irAE decreased to \leq Grade 1 after corticosteroid taper.

irAEs	Toxicity Grade (CTCAE v5.0)	Action With Study Intervention	Corticosteroid and/or Other Therapies	Monitoring and Follow-up
Pneumonitis	Grade 2	Withhold	Administer corticosteroids (initial dose of 1 to 2 mg/kg prednisone or equivalent)	 Monitor participants for signs and symptoms of pneumonitis Evaluate participants with suspected
	Recurrent Grade 2, Grade 3 or 4	Permanently discontinue	 followed by taper Add prophylactic antibiotics for opportunistic infections 	pneumonitis with radiographic imaging and initiate corticosteroid treatment
Diarrhea/Colitis	Grade 2 or 3	Withhold	 Administer corticosteroids (initial dose of 1 to 2 mg/kg prednisone or equivalent) followed by taper 	 Monitor participants for signs and symptoms of enterocolitis (ie, diarrhea, abdominal pain, blood or mucus in stool with or without fever) and of bowel perforation (ie, peritoneal signs and ileus) Participants with ≥Grade 2 diarrhea
	Recurrent Grade 3 or Grade 4	Permanently discontinue		 suspecting colitis should consider GI consultation and performing endoscopy to rule out colitis Participants with diarrhea/colitis should be advised to drink liberal quantities of clear fluids. If sufficient oral fluid intake is not feasible, fluid and electrolytes should be substituted via IV infusion

irAEs	Toxicity Grade (CTCAE v5.0)	Action With Study Intervention	Corticosteroid and/or Other Therapies	Monitoring and Follow-up
AST or ALT Elevation or Increased Bilirubin	Grade 2 ^a	Withhold	 Administer corticosteroids (initial dose of 0.5 to 1 mg/kg prednisone or equivalent) followed by taper 	 Monitor with liver function tests (consider weekly or more frequently until liver enzyme value returned to baseline or is stable)
	Grade 3 ^b or 4 ^c	Permanently discontinue	 Administer corticosteroids (initial dose of 1 to 2 mg/kg prednisone or equivalent) followed by taper 	
T1DM or Hyperglycemia	New onset T1DM or Grade 3 or 4 hyperglycemia associated with evidence of b-cell failure	Withhold ^d	 Initiate insulin replacement therapy for participants with T1DM Administer antihyperglycemic in participants with hyperglycemia 	 Monitor participants for hyperglycemia or other signs and symptoms of diabetes
Hypophysitis	Grade 2	Withhold	 Administer corticosteroids and initiate hormonal replacements as clinically indicated 	 Monitor for signs and symptoms of hypophysitis (including hypopituitarism and adrenal insufficiency)
	Grade 3 or 4	Withhold or permanently discontinue ^d		
Hyperthyroidism	Grade 2	Continue	 Treat with nonselective beta- blockers (eg, propranolol) or thionamides as appropriate 	 Monitor for signs and symptoms of thyroid disorders
	Grade 3 or 4	Withhold or permanently discontinue ^d		
Hypothyroidism	Grade 2, 3 or 4	Continue	 Initiate thyroid replacement hormones (eg, levothyroxine or liothyronine) per standard of care 	 Monitor for signs and symptoms of thyroid disorders

irAEs	Toxicity Grade (CTCAE v5.0)	Action With Study Intervention	Corticosteroid and/or Other Therapies	Monitoring and Follow-up
Nephritis: grading according to	Grade 2	Withhold	• Administer corticosteroids (prednisone 1 to 2 mg/kg or	• Monitor changes of renal function
increased creatinine or acute kidney injury	Grade 3 or 4	Permanently discontinue	equivalent) followed by taper	
Neurological Toxicities	Grade 2	Withhold	• Based on severity of AE administer corticosteroids	• Ensure adequate evaluation to confirm etiology and/or exclude other causes
	Grade 3 or 4	Permanently discontinue		
Myocarditis	Asymptomatic cardiac enzyme elevation with clinical suspicion of myocarditis (which was previously myocarditis Grade 1 using CTCAE v4.0)	Withhold	Based on severity of AE administer corticosteroids	 Ensure adequate evaluation to confirm etiology and/or exclude other causes
	Grade 2, 3 or 4	Permanently discontinue		
Exfoliative Dermatologic Conditions	Suspected SJS, TEN, or DRESS	Withhold	Based on severity of AE administer corticosteroids	• Ensure adequate evaluation to confirm etiology or exclude other causes
	Confirmed SJS, TEN, or DRESS	Permanently discontinue		

irAEs	Toxicity Grade (CTCAE v5.0)	Action With Study Intervention	Corticosteroid and/or Other Therapies	Monitoring and Follow-up
All Other irAEs	Persistent Grade 2	Withhold	Based on severity of AE administer corticosteroids	• Ensure adequate evaluation to confirm etiology or exclude other causes
	Grade 3	Withhold or discontinue based on the event ^e		
	Recurrent Grade 3 or Grade 4	Permanently discontinue		

AE(s)=adverse event(s); ALT= alanine aminotransferase; AST=aspartate aminotransferase; CTCAE=Common Terminology Criteria for Adverse Events; DRESS=Drug Rash with Eosinophilia and Systemic Symptom; GI=gastrointestinal; IO=immuno-oncology; ir=immune related; IV=intravenous; SJS=Stevens-Johnson Syndrome; T1DM=type 1 diabetes mellitus; TEN=Toxic Epidermal Necrolysis; ULN=upper limit of normal.

Note: Non-irAE will be managed as appropriate, following clinical practice recommendations.

- ^a AST/ALT: >3.0 to 5.0 x ULN if baseline normal; >3.0 to 5.0 x baseline, if baseline abnormal; bilirubin:>1.5 to 3.0 x ULN if baseline normal; >1.5 to 3.0 x baseline if baseline abnormal
- ^b AST/ALT: >5.0 to 20.0 x ULN, if baseline normal; >5.0 to 20.0 x baseline, if baseline abnormal; bilirubin:>3.0 to 10.0 x ULN if baseline normal; >3.0 to 10.0 x baseline if baseline abnormal
- ^c AST/ALT: >20.0 x ULN, if baseline normal; >20.0 x baseline, if baseline abnormal; bilirubin: >10.0 x ULN if baseline normal; >10.0 x baseline if baseline abnormal
- ^d The decision to withhold or permanently discontinue study intervention is at the discretion of the investigator or treating physician. If control achieved or \leq Grade 2, study intervention may be resumed.
- Events that require discontinuation include, but are not limited to, encephalitis and other clinically important irAEs (eg, vasculitis and sclerosing cholangitis).

Dose Modification and Toxicity Management of Infusion Reactions Related to MK-7684A or Atezolizumab

Administration of study intervention may cause severe or life-threatening infusion reactions including severe hypersensitivity or anaphylaxis. Signs and symptoms usually develop during or shortly after drug infusion and generally resolve completely within 24 hours of completion of infusion. Dose modification and toxicity management guidelines for the study intervention-associated infusion reaction are provided in Table 6.

		Premedication at Subsequent
NCI CTCAE Grade	Treatment	Dosing
Grade 1	Increase monitoring of vital signs as	None
Mild reaction; infusion	medically indicated until the participant	
interruption not indicated;	is deemed medically stable in the opinion	
intervention not indicated	of the investigator	
Grade 2	Stop Infusion	Participant may be premedicated
Requires therapy or	Additional appropriate medical therapy	1.5 h (± 30 min) prior to infusion of
infusion interruption but	may include but is not limited to:	study intervention with:
responds promptly to	IV fluids	Diphenhydramine 50 mg PO
symptomatic treatment	Antihistamines	(or equivalent dose of
(eg, antihistamines,	NSAIDs	antihistamine).
NSAIDs, narcotics, IV	Acetaminophen	Acetaminophen 500 to 1000 mg
fluids); prophylactic	Narcotics	PO (or equivalent dose of
medications indicated for	Increase monitoring of vital signs as	analgesic).
≤24 h	medically indicated until the participant	
	is deemed medically stable in the opinion	
	of the investigator.	
	If symptoms resolve within 1 hour of	
	stopping drug infusion, the infusion may	
	be restarted at 50% of the original	
	infusion rate (eg, from 100 mL/h to	
	50 mL/h). Otherwise dosing will be held	
	until symptoms resolve and the	
	participant should be premedicated for	
	the next scheduled dose.	
	Participants who develop Grade 2	
	toxicity despite adequate premedication	
	should be permanently discontinued from	
	further study intervention.	

Table 6	MK-7684A or Atezolizumab Infusion Reaction Dose Modification and
	Treatment Guidelines

08RNJZ

		Premedication at Subsequent
NCI CTCAE Grade	Treatment	Dosing
Grades 3 or 4	Stop Infusion.	No subsequent dosing
Grade 3:	Additional appropriate medical therapy	
Prolonged (ie, not rapidly	may include but is not limited to:	
responsive to	Epinephrine**	
symptomatic medication	IV fluids	
and/or brief interruption	Antihistamines	
of infusion); recurrence of	NSAIDs	
symptoms after initial	Acetaminophen	
improvement;	Narcotics	
hospitalization indicated	Oxygen	
for other clinical sequelae	Pressors	
(eg, renal impairment,	Corticosteroids	
pulmonary infiltrates)	Increase monitoring of vital signs as	
Grade 4:	medically indicated until the participant	
Life-threatening; pressor	is deemed medically stable in the opinion	
or ventilatory support	of the investigator.	
indicated	Hospitalization may be indicated.	
	**In cases of anaphylaxis, epinephrine	
	should be used immediately.	
	Participant is permanently discontinued	
	from further study intervention.	
CTCAE=Common Terminolog	y Criteria for Adverse Events; h=hour; IV=intrav	enous; NCI=National Cancer Institute;
NSAIDs= nonsteroidal anti-inf	lammatory drugs.	
Note: Appropriate resuscitatio	n equipment should be available at the bedside an	d a physician readily available during the
period of drug administrat	ion.	
For further information, p	lease refer to the Common Terminology Criteria	for Adverse Events v5.0 (CTCAE) at
http://ctep.cancer.gov		

Other Allowed Dose Interruption for MK-7684A or Atezolizumab

Study intervention may be interrupted for situations other than treatment-related AEs such as medical or surgical events and/or unforeseen circumstances not related to study intervention. However, study intervention is to be restarted within 3 weeks for Q3W, 21 days of the originally scheduled dose and within 42 days of the previously administered dose, unless otherwise discussed with the Sponsor. The reason for study intervention interruption is to be documented in the participant's study record.

08RNJZ

6.6.2 Management of Adverse Events and Dose Modifications for Etoposide/Platinum Chemotherapeutic Agents

If a participant experiences a $\geq 10\%$ weight change during Cycles 1 to 4, the doses of etoposide and cisplatin/carboplatin should be recalculated.

Study intervention-related toxicities must be resolved to baseline or Grade ≤ 1 before administering the next dose. Exceptions include alopecia, Grade 2 fatigue, and endocrine-related AEs requiring treatment or hormone replacement, which may be Grade ≤ 2 . For creatinine clearance, ANC, platelet, hemoglobin, total bilirubin, and AST/ALT, the guidelines provided below may be followed. Participants must not receive the next cycle of chemotherapy if any of the following apply:

- ANC <1,500/mm³
- Platelet count <100,000/mm³
- Hemoglobin level <8 g/dL
- Total bilirubin level $>1.5 \times ULN$
- AST and ALT levels $\geq 2.5 \times$ ULN, or $\geq 5 \times$ ULN if liver metastases are present

Dose modifications due to AEs will depend on the investigator's assessment of causality. and use a stepwise dose reduction according to Table 7. Recommended dose modifications for key chemotherapy toxicities (etoposide and cisplatin/carboplatin) are outlined in Table 8 and Table 9. These serve as a guide and do not replace investigator judgment and applicable local label recommendations, if more stringent. A participant is allowed to switch from cisplatin to carboplatin if the participant develops unexpected toxicities with the use of cisplatin (including hearing loss), becomes ineligible for further cisplatin therapy, and/or the investigator (after consultation with the Sponsor) considers switching to carboplatin to be in the best interest of the participant.

A maximum of 2 dose reductions per chemotherapy agent are permitted; if additional reductions are required, that particular agent must be discontinued. In the absence of the agent thought to be causing toxicity, treatment can continue with blinded study intervention with or without the remaining chemotherapeutic drug.

Once the dose has been decreased, it should remain reduced for all subsequent administrations or be further reduced, if necessary. There will be no dose escalations in this study.

	Etoposide	Cisplatin	Carboplatin
Dose Level 0 (starting dose)	100 mg/m ² /day	75 mg/m ²	AUC 5 mg/mL/min
Dose Level -1	75 mg/m ² /day	56 mg/m ²	AUC 4 mg/mL/min
Dose Level -2	50 mg/m²/day	38 mg/m ²	AUC 3 mg/mL/min
Dose Level -3	Discontinue	Discontinue	Discontinue

Table 7	Dose Modifications	for Chemothera	peutic Agents
10010 /	Dobe mounted	ioi chieniera	

Abbreviation: AUC=area under the curve

Table 8 F	Recommended	Chemotherapy	Dose Modi	fications fo	or Hematologic	^e Toxicity
-----------	-------------	--------------	-----------	--------------	----------------	-----------------------

Intervention-related Toxicity ^a	Etoposide	Cisplatin	Carboplatin
	Dose Le	evel (DL) from	Table 7
Neutrophils (ANC) <500/mm ³ without fever	DL -1	DL -1	DL -1
Febrile neutropenia (fever ≥38.5°C and ANC <1,000/mm ³)	DL -1	DL -1	DL -1
Platelets <50,000/mm ³ without significant bleeding or requiring packed platelet transfusion	DL -1	DL -1	DL -1
Platelets $<$ 50,000/mm ³ with Grade \ge 2 hemorrhage or requiring packed platelet transfusion	DL -2	DL -2	DL -2
Grade 4 anemia	DL -1	DL -1	DL -1
Abbreviations: ANC=absolute neutrophil count, DL=dose level			
Note: For grading, see CTCAE v5.0			

Note: If toxicity can clearly be attributed to one of the drugs, the investigator may choose to only reduce the dose of one of the chemotherapy agents. Investigators may decide to use supportive measures/treatment and/or secondary prophylaxis as per institutional standards (eg, filgrastim, pegfilgrastim, transfusions) instead of dose reductions for the next cycle, if considered in the best interest of the participant.

Should the hematologic toxicity recur, the dose of the agent could be reduced further. However, not more than 2 dose reductions per chemotherapy agent are permitted.

08RNJZ

Intervention-related Toxicity ^a	CTCAE Grade	Etoposide	Cisplatin	Carboplatin		
		Dose	Dose Level (DL) from Table 7			
Nausea/vomiting	Grade ≥3 ^b	DL 0	DL -1	DL -1		
Mucositis	Grade ≥3 ^b	DL -1	DL -1	DL -1		
Diarrhea	Grade $\geq 3^{b}$	DL -1	DL -1	DL -1		
	Grade 2	No modification	DL -1°	No modification		
Peripheral neuropathy	Grade 3	No modification	Discontinue ^d	DL -1		
	Grade 4	No modification	Discontinue	Discontinue		
	Grade 2	DL -2	No modification	No modification		
Total bilirubin	Grade 3	Discontinue	No modification	No modification		
	Grade 4	Discontinue	No modification	No modification		
	Grade 3	DL -1	DL -1	DL -1		
ASI of ALI Elevation	Grade 4	Discontinue	Discontinue	Discontinue		
Other nonhematologic toxicity (except fatigue and transient arthralgia and myalgia)	Grade ≥3	DL -1	DL -1	DL -1		

Table 9Recommended Chemotherapy Dose Modifications for Nonhematologic
Toxicity

ALT=alanine aminotransferase; AST=aspartate aminotransferase; CTCAE= Common Terminology Criteria for Adverse Events; DL=dose level

Note: If considered in the best interest of the participant, and consistent with local practice, investigators may decide to use supportive measures/treatment, and/or secondary prophylaxis instead of dose reductions for the next cycle. Also, if toxicity can clearly be attributed to one of the drugs, the investigator may choose to only reduce the dose of one of the chemotherapy agents.

- Should the toxicity recur, the dose of the agent could be reduced further. However, not more than 2 dose reductions per chemotherapy agent are permitted.
- This applies to toxicity of Grade 3 and lasting 72 hours or beyond despite aggressive supportive management, or toxicity of Grade 4.
- If Grade 2 neurotoxicity recurs after DL -1, drug will be given at DL -2 or switch can be made to the appropriate dose of carboplatin at the discretion of the investigator in consultation with the Sponsor. If Grade 2 neurotoxicity persists after 2 dose level reductions and 21-day hold, switch can be made to the appropriate dose of carboplatin at the discretion of the investigator in consultation with the Sponsor.
- ^d If Grade 3 neurotoxicity occurs, cisplatin will be discontinued and, upon improvement, a switch can be made to the appropriate dose of carboplatin at the discretion of the investigator in consultation with the Sponsor.

Creatinine clearance:

Creatinine clearance (CrCl) will be based on either the Cockcroft-Gault formula or another acceptable standard formula.

08RNJZ

For participants receiving cisplatin, the scheduled dose of cisplatin may only be administered if the calculated CrCl is \geq 50 mL/min:

- If CrCl falls to <50 mL/min, delay the start of that cycle for ≤21 days. In the interim, monitor renal function weekly and consider IV hydration. When CrCl improves to ≥50 mL/min, decrease cisplatin to DL -1. Alternatively, if in the investigator's judgment it is in the best interest of the participant, cisplatin can be switched to carboplatin if the calculated CrCl is appropriate, and in consultation with the Sponsor.
- At the second occurrence of CrCl <50 mL/min, decrease cisplatin to DL -2 upon improvement of CrCl to ≥50 mL/min. Alternatively, if in the investigator's judgment it is in the best interest of the participant, cisplatin can be switched to carboplatin if the calculated CrCl is appropriate, and in consultation with the Sponsor.
- At the third occurrence of CrCl <50 mL/min, cisplatin should be discontinued. If in the investigator's judgment it is in the best interest of the participant, cisplatin can be switched to carboplatin if the calculated CrCl is appropriate, at the discretion of the investigator and in consultation with the Sponsor.

For participants receiving carboplatin, the scheduled of carboplatin may only be administered if the calculated CrCl is \geq 40 mL/min:

- If CrCl falls to <40 mL/min, delay the start of that cycle for ≤21 days. In the interim, monitor renal function weekly and consider IV hydration. When CrCl improves to ≥40 mL/min, decrease carboplatin to DL -1.
- At the second occurrence of CrCl <40 mL/min, decrease carboplatin to DL -2 upon improvement of CrCl to ≥40 mL/min.
- At the third occurrence of CrCl <40 mL/min, carboplatin should be discontinued.

For participants receiving etoposide, the full dose of etoposide may only be administered if the calculated CrCl is \geq 50 mL/min. If CrCl falls between 15 mL/min and <50 mL/min, then participants should receive only 75% of the recommended dose.

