- 7. Has measurable disease per RECIST 1.1 as assessed by the local site investigator/radiology. Lesions situated in a previously irradiated area are considered measurable if progression has been shown in such lesions. At least 1 lesion that meets the criteria for being measurable, as defined by RECIST 1.1, must be appropriate for selection as a target lesion.
- 8. Note: for the purposes of this study, metastatic lesions situated in the brain are not considered measurable and should be considered non-target lesions.
- 9. Submits a pretreatment archival tumor tissue sample or newly obtained core, incisional, or excisional biopsy of a tumor lesion not previously irradiated where such sample exists. Biopsy/tissue is preferred, but cytology sample by fine needle aspiration is allowed. The sample may be submitted after enrollment but must be submitted within 4 weeks after randomization. Details pertaining to tumor tissue submission can be found in the Laboratory Manual.
- 10. Has an ECOG performance status of 0 to 1 assessed within 7 days before allocation/randomization.
- 11. Has adequate organ function as defined in the following table (Table 3). Specimens must be collected within 7 days before the start of study intervention.

System	Laboratory Value
Hematological	
Absolute neutrophil count (ANC)	$\geq 1500/\mu L$
Platelets	≥100 000/µL
Hemoglobin	\geq 8.0 g/dL or \geq 5.0 mmol/ ^a
Renal	
Measured or calculated ^b creatinine clearance	≥60 mL/min for participant receiving cisplatin ≥50 mL/min for participants receiving carboplatin
Hepatic	
Total bilirubin	\leq 1.5 ×ULN OR direct bilirubin \leq ULN for participants with total bilirubin levels >1.5 × ULN
AST (SGOT) and ALT (SGPT)	\leq 2.5 × ULN (\leq 5 × ULN for participants with liver metastases)
Coagulation	
International normalized ratio (INR) OR prothrombin time (PT) Activated partial thromboplastin time (aPTT)	\leq 1.5 × ULN unless participant is receiving anticoagulant therapy as long as PT or PTT is within therapeutic range of intended use of anticoagulants

Table 3Adequate Organ Function Laboratory Values

ALT (SGPT)=alanine aminotransferase (serum glutamic pyruvic transaminase); AST (SGOT)=aspartate aminotransferase (serum glutamic oxaloacetic transaminase); GFR=glomerular filtration rate; ULN=upper limit of normal.

^a Criteria must be met without erythropoietin dependency and without packed red blood cell (pRBC) transfusion within last 2 weeks.

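### Section 6.6.2: the AST/ALT line in the mandatory chemotherapy hold list literally needs both enzymes raised; a limit for each enzyme is very probably intended

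*Combined protocol and SAP*

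**What the plan says.** The hold list in Section 6.6.2 opens with "Participants must not receive the next cycle of chemotherapy if any of the following apply". Four items follow with one parameter each (neutrophils, platelets, hemoglobin, total bilirubin). The fifth names two enzymes: "AST and ALT levels $\geq 2.5 \times$ ULN, or $\geq 5 \times$ ULN if liver metastases are present".

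Two sentences before the list bear on it. One is a general recovery rule: "Study intervention-related toxicities must be resolved to baseline or Grade" 1 or lower before the next dose. The other says that, for creatinine clearance, the blood counts, bilirubin and AST/ALT, the guidance that follows can be used. It does not say whether this replaces the recovery rule for those parameters or adds to it.

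Elsewhere:

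- Table 3 (Section 5.1) sets an entry limit for "AST (SGOT) and ALT (SGPT") at the same 2.5 and 5 x ULN, as a ceiling.
- Table 5 has a row for "AST or ALT Elevation or Increased Bilirubin". Its footnote a defines Grade 2 as "AST/ALT: >3.0 to 5.0 x ULN if baseline normal; >3.0 to 5.0 x baseline, if baseline abnormal".
- Table 9, headed "Intervention-related Toxicity", acts on elevation of either enzyme (allowing for an evident PDF misread of the row label). It starts at Grade 3 with a one-level dose reduction and discontinues at Grade 4.
- Section 8.4.7 defines its hepatic event of clinical interest by a rise in either enzyme, together with bilirubin and alkaline phosphatase criteria.

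**The concern.** Table 3 uses *and* correctly, because both enzymes must lie at or below the ceiling. The negation of that condition is that either enzyme lies above it. The hold list takes the same two limits and reverses the inequality, but keeps *and*. As a stopping condition, the line then literally fires only when both enzymes are raised.

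A compulsory safety hold should have one reading. As the line stands, the same laboratory report can be either a required hold or a matter for investigator review and the product label. Section 9.11 has departures from directed administration reported, so the reading also decides whether a cycle given with one raised enzyme counts as such a departure.

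**Working it through.** The plan states no figure to reproduce. The check is one of logic, with values in multiples of ULN.

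**Inputs.** L is the list limit: 2.5, or 5 with liver metastases (Section 6.6.2). B is the enzyme's baseline. R is the grading reference: 1 if baseline is normal, B if abnormal (Table 5 footnotes). Grade 2 is above 3.0R to 5.0R, Grade 3 above 5.0R to 20.0R, Grade 4 above 20.0R (footnotes a to c). I assume the same grades apply in Section 6.6.2.

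**Rules compared.** Literal: AST ≥ L and ALT ≥ L. Per enzyme: AST ≥ L or ALT ≥ L. The last two columns apply to intervention-related rises. In rows 2 and 3 the AST baseline is normal.

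| Case | Literal hold | Per-enzyme hold | Highest grade | Recovery rule, if it governs AST/ALT | Table 9 |
|---|---|---|---|---|---|
| 1. No liver metastases, normal baselines, AST 2.7, ALT 0.8 | no | yes | below 2 | no hold | none |
| 2. No liver metastases, ALT 4.0 from baseline 1.5 (4.0/1.5 = 2.67), AST 2.0 | no | yes | below 2 | no hold | none |
| 3. Liver metastases, ALT 5.5 from baseline 2.0 (5.5/2.0 = 2.75), AST 2.5 | no | yes | below 2 | no hold | none |
| 4. No liver metastases, normal baselines, AST 4.0, ALT 0.8 | no | yes | 2 | hold | none |
| 5. Liver metastases, normal baselines, AST 6.0, ALT 0.8 | no | yes | 3 | hold | one-level reduction |
| 6. No liver metastases, normal baselines, AST 21, ALT 0.8 | no | yes | 4 | hold | discontinue |

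**If the recovery rule still governs AST/ALT.** A related isolated rise x meets no numeric hold when L ≤ x ≤ 3.0R. Such a range exists only if 3.0R ≥ L.

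- No liver metastases, normal baseline: 2.5 to 3.0.
- No liver metastases, abnormal baseline: 2.5 to 3.0B. For B = 1.5 this is 2.5 to 4.5. At the Table 3 entry ceiling, B = 2.5, the theoretical top is 3.0 x 2.5 = 7.5.
- Liver metastases, normal baseline: no gap, because 5 exceeds 3.0 and is already Grade 2.
- Liver metastases, abnormal baseline: a gap only if B ≥ 5/3 = 1.67. For B = 2.0 it is 5 to 6. At the entry ceiling, B = 5, the theoretical top is 3.0 x 5 = 15.

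**If the second sentence takes AST/ALT out of that rule.** The upper bounds disappear. Any isolated rise at or above L meets no numeric hold, including with liver metastases and a normal baseline (row 5). Row 4 then meets neither a hold nor a Table 9 action. Rows 5 and 6 meet only the Table 9 reduction or discontinuation.

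**Rises judged unrelated.** The recovery rule and Table 9 cover only intervention-related toxicity, so on the literal reading an unrelated isolated rise meets no numeric hold under either interpretation. This should be uncommon, since Section 10.3.5 generally assigns causality to the whole regimen.

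**Other provisions.** Table 5 withholds the blinded drug for an immune-related Grade 2 rise, but Section 6.6.2.2 lets chemotherapy go on when only the blinded drug is held. Pre-dose review of results (Section 8.3.5.1, Appendix 2) and the product labels (Sections 6.2.1 and 6.6.2) set no AST/ALT limit in the protocol text.

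**The case against.** The strongest reply is that the line has only one sensible meaning. The hold list mirrors Table 3 parameter by parameter, Table 3's ceiling plainly applies to each enzyme, the plural *levels* fits that sense, and the tables and Section 8.4.7 treat either enzyme as enough. That stands as the better reading in context. It does not change the literal condition in an instruction that must not be breached, and the sponsor's intent remains an inference.

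Second, clinicians are not left without safeguards. Results must be reviewed and found acceptable before each dose, labels apply, and Section 7.1 provides for stopping treatment that puts a participant at unnecessary risk. Section 6.6.2 adds that its recommended modifications "do not replace investigator judgment and applicable local label recommendations, if more stringent". This limits the consequence, but none of it supplies a numeric AST/ALT hold.

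Third, the permissive sentence before the list sits uneasily with the list's own prohibition, and changing one conjunction does not settle that. This is fair. The proposed change settles only which enzyme pattern triggers the hold.

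A reader might go further and infer that participants were dosed unsafely, or that the safety or efficacy results are compromised. The documents do not support this: they give no count of isolated rises and do not show which reading sites applied.

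**Conclusion.** The point holds as a minor drafting error in a mandatory safety rule. That a per-enzyme limit was intended is very probable but not stated. The size of the gap is conditional. It is bounded by 3.0 x ULN or 3.0 x baseline if the recovery rule still governs AST/ALT, and has no upper bound if it does not. It would therefore be wrong to treat either the narrow 2.5 to 3.0 x ULN band, or the absence of a gap with liver metastases and a normal baseline, as settled. Both rest on an interpretation the text leaves open.

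No number of affected participants can be derived. The present effect is very small: chemotherapy was limited to Cycles 1 to 4, Arm A is discontinued, continuing treatment is atezolizumab managed per local label (Section 6.6), and Amendment 05 keeps the older text for historical reference. No endpoint, alpha or power is affected.

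**What to change.** In this one line of Section 6.6.2, change *AST and ALT levels* to *AST or ALT level*. Leave the inequality sign and both limits as they are. Tables 3, 5 and 9 and Section 8.4.7 need no change. Every case in the table above is then held by the list itself, whichever way the recovery rule is read and whatever the attribution. The cost is one conjunction and a singular noun in the text and, in practice, an occasional cycle delayed for an isolated enzyme rise, which the per-enzyme reading already requires.
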